4.3.1.3. Change from Baseline in eGFR at Weeks 26 and 50 (Both Cohorts)

Kidney function evaluated by eGFR will be calculated based on the Chronic Kidney Disease Epidemiology Collaboration (CKD-EPI) formula. For participants requiring dialysis for acute kidney injury, a value of 10 mL/min/1.73 m² will be imputed for while participants are on dialysis (ie, from the first day of dialysis through 5 days after the end of dialysis).

For participants in the LN cohort, baseline eGFR will be defined as the lowest measurement available prior to the first dose of study intervention. For participants in the IgAN cohort, baseline eGFR will be defined as the mean of the Screening and Day 1 measurements.

The longitudinal changes in eGFR will be analyzed using the same MMRM method specified in Section 4.3.1.1, but the log-transformation of eGFR is not required. The eGFR will be summarized at baseline and at Weeks 26 and 50 by treatment group using descriptive statistics for the observed value as well as the change from baseline. No formal treatment comparison will be made. The point estimate and 2-sided 95% CI for the change from baseline of eGFR will be presented.

For the IgAN cohort, a similar summary will be made and the change from re-baseline (ie, Week 26) in eGFR at Week 50 will also be presented for each treatment sequence group from the MMRM analysis.

The data after the intercurrent events will be treated as missing.

In addition to the MMRM analysis, observed values, change from baseline, and percent change from baseline in eGFR will be summarized descriptively by treatment group at baseline and each post-Baseline time point separately by study phase.

The trajectory of eGFR over time will be visually presented by plotting the mean eGFR at each time point by treatment group.

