4.3. Secondary Endpoint Analysis

The secondary efficacy analyses will be based on the FAS. These analyses will be descriptive in nature and no adjustment for multiplicity will be performed.

The analyses for participants in the LN cohort and participants in the IgAN cohort will be conducted and reported separately. Participants in each disease-specific cohort will be analyzed as randomized, regardless of actual treatment received.

The estimands for the key secondary analyses are defined in Table 6.

Table 6: Estimands for Key Secondary Analyses

Estimand	Population	Variable	Intercurrent Event	Population-level Summary
Key secondary analysis (continuous)	FAS	 Percentage change in proteinuria from baseline to Week 50 (both cohorts) Change from baseline in eGFR at Weeks 26 and 50 (both cohorts) 	 Receipt of additional standard-of-care therapy for a protocol-defined renal flare or suboptimal response (LN cohort only) Treatment discontinuation 	 Mean difference of percentage change in proteinuria from baseline in each treatment group Mean change in eGFR from baseline in each treatment group
Key secondary analysis (binary)	FAS	 Achieving > 30% and > 50% reduction in proteinuria at Weeks 26 and 50 compared to baseline (both cohorts) Meeting the criteria for CRR at Weeks 26 and 50 (LN cohort only) Meeting the criteria for PRR at Weeks 26 and 50 (LN cohort only) Meeting the criteria for partial remission at Weeks 26 and 50 (IgAN cohort only) 	Receipt of additional standard-of-care therapy for a protocol-defined renal flare or suboptimal response (LN cohort only) Treatment discontinuation	Response rate in each treatment group

Abbreviations: CRR = complete renal response; eGFR = estimated glomerular filtration rate; FAS = Full Analysis Set; LN = lupus nephritis; PRR = partial renal response

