4.3.1.4. Complete Renal Response (LN Cohort Only)

Complete renal response (CRR) will be assessed at Weeks 26 and 50. To achieve CRR, participants in the LN cohort must meet all of the following criteria:

- A decrease in mean UPCR to ≤ 0.5 g/g based on two 24-hour urine collections obtained within 2 weeks prior to the study visit (Week 26 or 50)
- eGFR > 60 mL/min/1.73 m² or no eGFR reduction ≥ 20% from the baseline value based on the mean of 2 values. The first eGFR value must be obtained within 2 weeks prior to the study visit (Week 26 or 50) and the second eGFR value will be obtained on the study visit (Week 26 or 50)
- No treatment failure (as defined in Section 4.3.1.10)

The percentage of participants meeting the criteria for CRR as well as individual components of CRR will be summarized at Weeks 26 and 50 by treatment group by calculating the point estimate and 2-sided 95% CI, based on exact confidence limits using the Clopper-Pearson method.

Study participants with treatment discontinuation will be treated as failure to meet CRR criteria and considered nonresponders.

A bar chart will also be provided displaying the proportion of participants meeting the criteria for CRR as well as individual components of CRR at Weeks 26 and 50 by treatment group.

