4.4.2. Change from Baseline in eGFR at Weeks 102 and 154 (Both Cohorts)

The analysis will be performed at Weeks 102 and 154 using the same approach as defined in Section 4.3.1.3. Results will be presented for each treatment sequence group.

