6.1.2. Definition of Baseline Values

For the 26-week Blinded Initial Evaluation Period, baseline is defined as the last available assessment value prior to the first dose of study intervention. For the 24-week Blinded Extended Treatment Period, a re-baseline is defined as the last available assessment prior to the first dose of study intervention administered in the extension period.

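### The LN baseline eGFR is the lowest pre-dose value, which shifts the reported within-arm eGFR change upward in every LN arm

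*SAP*

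**What the plan says.** SAP 4.3.1.3 gives the LN rule: "baseline eGFR will be defined as the lowest measurement available prior to the first dose of study intervention". It sets no look-back window, no limit on the number of values and no reason. The next sentence uses a different rule for IgAN: "baseline eGFR will be defined as the mean of the Screening and Day 1 measurements". The general rule in SAP 6.1.2 is different again: "baseline is defined as the last available assessment value prior to the first dose of study intervention". Section 6.1.2 lists no exceptions, and SAP 4.8 (changes to protocol-planned analyses) does not mention the LN rule. Protocol 9.4.6.2.1 plans a summary of eGFR change from baseline without a lowest-value rule.

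SAP Table 6 lists eGFR change at Weeks 26 and 50 as a key secondary estimand, summarised as "Mean change in eGFR from baseline in each treatment group". On reporting, 4.3.1.3 says: "The point estimate and 2-sided 95% CI for the change from baseline of eGFR will be presented". On comparison it says: "No formal treatment comparison will be made". SAP 4.4.2 extends the analysis to Weeks 102 and 154 "using the same approach as defined in Section 4.3.1.3".

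The eGFR component of CRR and PRR (SAP 4.3.1.4 and 4.3.1.5, Protocol 8.1.10) asks for eGFR above 60 or "no eGFR reduction ≥ 20% from the baseline value based on the mean of 2 values". Neither document says which eGFR baseline that is.

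**The concern.** Baseline and follow-up are built differently. Baseline is the worst of two or more readings. Under SAP 6.1.6, follow-up is the one reading closest to the scheduled day. Choosing the worst reading picks up downward measurement noise that the follow-up reading does not share, so a participant whose kidney function never changed will on average appear to improve.

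If the between-arm difference were the headline, this would matter little, since the rule uses only pre-dose data and affects all arms alike. Here the within-arm change is the defined estimand and the quantity given a confidence interval. An LN arm with stable function could be read as having gained eGFR, and the LN and IgAN results would not be on the same footing. If the same baseline governs CRR and PRR, their eGFR component also becomes easier to pass.

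**Working it through.** **Inputs.** From the documents: two scheduled LN pre-dose eGFR values (Protocol Table 1, Screening and Day 1), with creatinine drawn before dosing (Protocol 8.1.3); 30 participants in each of the 180 mg and placebo arms and 10% dropout (Protocol 9.2), giving 30 × 0.9 = 27 per arm. The documents give no eGFR SD or expected change, so there is no stated figure to reproduce. Assumed: within-person SD of one reading s = 5 to 15; SD of true change 15 to 20 (all mL/min/1.73 m²).

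**Direction.** The minimum of a set cannot exceed its mean or its last member. No participant's change can be lower under this rule than under either alternative, and an arm's mean is strictly higher once one participant's two readings differ.

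**Size, stable level.** For two independent normal readings, E[min] = mean − s/√π = mean − 0.564s. For three, simulation gives mean − 0.846s.

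| s | Shift, 2 values | Shift, 3 values |
|---|---|---|
| 5 | 2.8 | 4.2 |
| 8 | 4.5 | 6.8 |
| 10 | 5.6 | 8.5 |
| 15 | 8.5 | 12.7 |

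**Does the baseline covariate remove it?** No. I simulated a 30/10/30 trial with no true change, s = 5, and a single-visit model with arm and baseline. The LS-mean changes for placebo, 120 mg and 180 mg were 2.82, 2.83 and 2.82 under the lowest-value rule, and at most 0.01 under the last or mean value. The 180 mg minus placebo contrast was 0.003, so it is unbiased.

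**Coverage of the nominal 95% CI** (n = 27, true mean change 0, 40,000 simulated arms). Worked example with s = 8 and SD of true change 15:
- Variance of a change = 225 + 64 + 64(1 − 1/π) = 332.6, so the SD is 18.2.
- SE = 18.2/√27 = 3.5.
- The shift of 4.5 is about 1.3 standard errors.

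| s | Lowest value | Mean or last value |
|---|---|---|
| 5 | 86–90% | 95% |
| 8 | 77–83% | 95% |
| 10 | 70–78% | 95% |
| 15 | 59–67% | 95% |

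The ranges run from SD of true change 15 to 20.

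**If true eGFR moves by d from Screening to Day 1.** Let D ~ N(d, 2s²). Then mean − min = E|D|/2 and last − min = E|D|/2 + d/2. For s = 8:

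| d | Mean − min | Last − min |
|---|---|---|
| −10 | 6.2 | 1.2 |
| 0 | 4.5 | 4.5 |
| +10 | 6.2 | 11.2 |

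**CRR/PRR eGFR component, only if the same baseline applies.** In an assumed cohort (true eGFR mean 80, SD 30, Screening value above 30, no mean change, SD of true change 15), the pass rate rises by about 1.6 to 3.7 percentage points for s = 5 to 15 relative to the two-value mean. The gain arises only among the roughly 23% with follow-up eGFR of 60 or below. The effect on full CRR or PRR is smaller, because the UPCR criterion and absence of treatment failure are also required.

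**The case against.** The strongest reply is that the rule may be deliberate. LN participants enter with active disease, and some start corticosteroid induction during Screening, so the pre-dose low could serve as a flare-level reference. If the target is change from the true lower of the two levels, the bias shrinks as the levels separate. With s = 8 and SD of true change 15 it is 4.5, 2.4 and 1.2 at d = 0, 5 and 10, with coverage of about 77%, 90% and 94%. On that view most of the 11.2 gap at d = +10 is real movement. This is sound arithmetic, but the documents do not state that target, and a selection shift remains, largest where function is stable or the readings are noisy.

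Several other points stand:
- The secondary analyses are descriptive, and within-arm change mixes drug with standard of care under any baseline.
- The arms share the shift, so a reader who compares arms is not misled. SAP 4.1 mentions a 90% CI for observed differences in general, although 4.3.1.3 names no between-arm eGFR difference.
- The conflict with 6.1.2 is weak evidence alone: an endpoint-specific rule can override a general one, and 6.1.2 also omits the IgAN mean rule. That settles precedence, not the shift.
- Values of s near 15 are the unfavourable end of an assumed range.
- The CRR/PRR effect is conditional and, at 1.6 to 3.7 points, about 0.5 to 1 participant per arm of 30.

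**Conclusion.** The concern holds. The direction is certain; the size depends on a within-person SD that the documents do not give. For s between 5 and 10, with two independent readings around a stable level, the reported mean change in each LN arm is too high by 2.8 to 5.6 mL/min/1.73 m², and the nominal 95% CI covers the true change in roughly 70–90% of trials. Further unscheduled readings enlarge the shift; a participant with only one pre-dose value has none. The primary proteinuria endpoint and the 180 mg versus placebo eGFR contrast are unaffected. The point deserves correction because the distorted quantity is the defined estimand and the one reported, at Weeks 26 and 50 and by cross-reference at Weeks 102 and 154. For CRR and PRR the firm finding is only that the eGFR baseline is unspecified.

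**What to change.** Before the sponsor is unblinded for the Week 26 analysis:

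1. Define LN baseline eGFR as the mean of the Screening and Day 1 central-laboratory values, matching IgAN, or as the last pre-dose value, matching SAP 6.1.2.
2. State that this definition governs 4.3.1.3, 4.4.2, CRR and PRR, and list any exception in 6.1.2.
3. Keep the lowest-value version as a sensitivity summary.
4. Report the 180 mg minus placebo eGFR difference with its CI, descriptively, from the MMRM already planned.

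If unblinding has already happened, report both versions and label the change post hoc.

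The cost is short edits to SAP 4.3.1.3, 4.3.1.4, 4.3.1.5 and 6.1.2, one sensitivity table and one model contrast, with no new data. The drawback is that, for participants who start corticosteroid induction during Screening, the two-value mean can blend two disease states; the sensitivity summary shows how much that matters.

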4.3.1.4. Complete Renal Response (LN Cohort Only)

Complete renal response (CRR) will be assessed at Weeks 26 and 50. To achieve CRR, participants in the LN cohort must meet all of the following criteria:

- A decrease in mean UPCR to ≤ 0.5 g/g based on two 24-hour urine collections obtained within 2 weeks prior to the study visit (Week 26 or 50)
- eGFR > 60 mL/min/1.73 m² or no eGFR reduction ≥ 20% from the baseline value based on the mean of 2 values. The first eGFR value must be obtained within 2 weeks prior to the study visit (Week 26 or 50) and the second eGFR value will be obtained on the study visit (Week 26 or 50)
- No treatment failure (as defined in Section 4.3.1.10)

The percentage of participants meeting the criteria for CRR as well as individual components of CRR will be summarized at Weeks 26 and 50 by treatment group by calculating the point estimate and 2-sided 95% CI, based on exact confidence limits using the Clopper-Pearson method.

Study participants with treatment discontinuation will be treated as failure to meet CRR criteria and considered nonresponders.

A bar chart will also be provided displaying the proportion of participants meeting the criteria for CRR as well as individual components of CRR at Weeks 26 and 50 by treatment group.

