Figure 2:	Study Design Schematic (IgAN Cohort)	18

VERSION HISTORY

This statistical analysis plan (SAP) for Study ALXN2050-NEPH-201 is based on Protocol Amendment 3.0, dated 21 Feb 2024.

SAP Version	Version Date	Change	Rationale
1.0	23 Nov 2022	Not applicable	Original version.
2.0	10 May 2023	Included the option to perform an early interim analysis	For Phase 3 planning purposes.
		Other minor edits	For clarity.
3.0	12 Nov 2024	Deleted data presentation for Safety Follow-up Period	Safety Follow-up Period is not a treatment period.
		Revised the derivation of the primary endpoint	Visit window is changed.
		Added ALXN2050 Total group into data presentation	To evaluate the overall ALXN2050 treatment effect.
		Changed terminologies: "background therapy" to "allowed concomitant therapy" and "rescue therapy" to "additional standard-of-care therapy"	To align with EU CTR requirements.
		Added an analysis of abnormal liver enzyme elevations	To evaluate drug-induced liver injury.
		Added a sensitivity analysis due to dosing pause	Screening, enrollment, and study intervention administration have been temporarily paused as of 06 September 2024.
		Other minor edits	For minor corrections.

APPROVAL SIGNATURES

Biostatistics	Date dd Mmm yyyy
Biostatistics	Date dd Mmm yyyy
	Date dd Mmm yyyy

LIST OF ABBREVIATIONS

Abbreviation	Definition
AE	adverse event
ALP	alkaline phosphatase
ALT	alanine aminotransferase
AP	alternative pathway
AST	aspartate aminotransferase
ATC	anatomical therapeutic chemical
Bb	Bb fragment of complement factor B
bid	twice daily
BLQ	below the limit of quantification
Clq	complement component C1q
C3	complement component 3
C4	complement component 4
CDF	cumulative distribution function
CI	confidence interval
CNI	calcineurin inhibitor
COVID-19	coronavirus disease 2019
CRR	complete renal response
cTTO	composite time trade-off
CV	coefficient of variation
CV%	coefficient of variation percentage
dsDNA	double-stranded DNA
EC	exclusion criteria
ECG	electrocardiogram
eCRF	electronic case report form
eGFR	estimated glomerular filtration rate
EQ-5D-5L	5-level EuroQol-5 Dimensions
FACIT-Fatigue	Functional Assessment of Chronic Illness Therapy – Fatigue Scale
FAS	Full Analysis Set
FD	factor D
GM	geometric mean
GMR	geometric mean ratio
hpf	high power field
IC	inclusion criteria
IE	intercurrent event

Abbreviation	Definition	
IgAN	immunoglobulin A nephropathy	
LLN	lower limit of normal	
LN	lupus nephritis	
MAR	missing-at-random	
MCS	Mental Component Summary	

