4.2.1. Derivation of Endpoint(s)

The primary endpoint for the study is percentage change from baseline to Week 26 in proteinuria based on 24-hour urine collection(s) at each time point.

Proteinuria will be measured by absolute urine protein (UP) in g/day as well as by urine protein-to-creatinine ratio (UPCR) in g/g for each disease cohort as follows:

- For the LN cohort, proteinuria measured by UPCR as well as by UP is derived from a single 24-hour urine collection at Screening and the mean of 2 separate 24-hour urine collections within 3 weeks prior to or 1 week after Week 26 Visit to assess the primary endpoint. Two separate 24-hour collections should be obtained at Week 50 Visit to assess the secondary endpoint, as long as they are collected within 3 weeks prior to Week 50 Visit. Additional 24-hour urine collections are also scheduled for Weeks 102 and 154.
- For the IgAN cohort, proteinuria measured by UP as well as UPCR is derived from the mean of 2 valid 24-hour urine collections during the Screening Period and within 3 weeks prior to Week 26 Visit to assess the primary endpoint. Two separate 24-hour collections should be obtained at Week 50 Visit to assess the secondary endpoint, as long as they are collected within 3 weeks prior to or 1 week after Week 50 Visit. Additional 24-hour urine collections are also scheduled for Weeks 102 and 154.

For the primary endpoint, proteinuria will be based on UPCR for the LN cohort and UP for the IgAN cohort. For both cohorts, the natural logarithm will be used to transform proteinuria values before the analysis to reduce skewness. When 2 valid 24-hour urine collections are required and only 1 valid collection is available at the visit, then this value will be used for analysis.

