4.3.1.13. Partial Remission (IgAN Cohort Only)

For the IgAN cohort, partial remission will be defined as mean proteinuria < 1 g/24 hours based on 2 valid 24-hour urine collections obtained within 2 weeks prior to the study visit (Week 26 or 50).

The percentage of participants meeting the criteria for partial remission will be summarized at Weeks 26 and 50 by treatment group by calculating the point estimate and 2-sided 95% CI based on exact confidence limits using the Clopper-Pearson method.

Participants who discontinue treatment prior to the endpoint will be treated as failure to meet partial remission criteria and considered nonresponders.

A bar chart will also be provided displaying the proportion of participants meeting the criteria for partial remission at Weeks 26 and 50 by treatment group.

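### SAP 4.2.1 accepts 24-hour urine from up to 3 weeks before the visit, but CRR, PRR and IgAN partial remission keep a 2-week window for the same measurements

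*SAP*

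**What the plan says.** **Proteinuria (SAP 4.2.1).** The windows differ by cohort and visit:
- LN, Week 26: "the mean of 2 separate 24-hour urine collections within 3 weeks prior to or 1 week after Week 26 Visit".
- IgAN, Week 26: two valid collections "during the Screening Period and within 3 weeks prior to Week 26 Visit to assess the primary endpoint".
- LN, Week 50: two collections, "as long as they are collected within 3 weeks prior to Week 50 Visit".
- IgAN, Week 50: two collections, "as long as they are collected within 3 weeks prior to or 1 week after Week 50 Visit".

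If only one valid collection exists at a visit, 4.2.1 uses that value.

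**Responses.** CRR in SAP 4.3.1.4 is "based on two 24-hour urine collections obtained within 2 weeks prior to the study visit (Week 26 or 50". PRR (4.3.1.5) has the same window. IgAN partial remission (4.3.1.13) is "based on 2 valid 24-hour urine collections obtained within 2 weeks prior to the study visit". The derivation sections 6.1.8, 6.1.10 and 6.1.11 repeat the 2 weeks. They use a single value when only one collection is available at the visit, and set the response to missing when both are missing.

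**Where the difference comes from.** The protocol uses 2 weeks before the visit both for the Week 26 and Week 50 proteinuria collections (8.1.1.1, 8.1.1.2) and for the responses (8.1.10, 8.1.11). The SAP version history for v3.0 records "Revised the derivation of the primary endpoint" and gives a changed visit window as the reason. SAP 4.8, which lists departures from the protocol's analyses, mentions only hematuria.

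**The concern.** The responses use the same measurements as the primary endpoint: 24-hour UPCR in LN and 24-hour protein in IgAN. Under the protocol one window served all of them. Under SAP v3.0 a collection can count for percentage change in proteinuria and fall outside the response criterion at the same visit. The endpoints of more than 30% and more than 50% reduction (4.3.1.2) state no window of their own, so 4.2.1 is the natural rule for them. A participant could then be a more-than-50% reducer and have no PRR status.

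The SAP also conflicts with itself in the dosing-pause analyses. The population of no impact by dosing pause (4.2.3) admits anyone with a valid collection within 3 weeks before Week 26 and before the pause. Sections 4.3.2.4 to 4.3.2.6 use that population for CRR, PRR and partial remission. A participant can enter it on a collection 15 to 21 days before the visit that the response definition does not accept.

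At stake are usable data, and denominators that differ between endpoints describing the same urine.

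**Working it through.** The plan gives no figure on this point to reproduce, and no stated power or alpha depends on it. The check is a day count, then a bound on the effect.

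**Day counts.** The nominal visit days are 183 and 351 (protocol 1.3). Number of days = last − first + 1, visit day included. The 2-week window is Days 183 − 14 = 169 to 183, or 351 − 14 = 337 to 351, which is 15 days each.

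| Cohort, visit | Proteinuria window (4.2.1) | Response window | Valid for proteinuria only |
|---|---|---|---|
| LN, Week 26 | Days 162–190, 29 days | Days 169–183 | Days 162–168 and 184–190: 14 of 29 |
| IgAN, Week 26 | Days 162–183, 22 days | Days 169–183 | Days 162–168: 7 of 22 |
| LN, Week 50 | Days 330–351, 22 days | Days 337–351 | Days 330–336: 7 of 22 |
| IgAN, Week 50 | Days 330–358, 29 days | Days 337–351 | Days 330–336 and 352–358: 14 of 29 |

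These are shares of calendar days, not of participants.

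**Consequences on the literal reading, for a participant with two collections valid under 4.2.1:**
- Both within 2 weeks: both endpoints use the same two values.
- One outside: proteinuria is the mean of two, and the response rests on one.
- Both outside: proteinuria is available, and the response is missing.

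The SAP does not say how a missing response counts. Sections 4.3.1.4 and 4.3.1.5 make treatment discontinuation a nonresponse, and 4.1.4 imputes nothing for missing data not due to intercurrent events.

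**Effect of one participant, arm size n with x responders:**
- Responder counted as nonresponder: change = 1/n.
- Responder excluded: x/n − (x − 1)/(n − 1) = (n − x)/[n(n − 1)], at most 1/n.
- Nonresponder excluded: x/(n − 1) − x/n = x/[n(n − 1)], also at most 1/n.

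The ceiling is 1/30 = 3.3 points (LN) and 1/24 = 4.2 points (IgAN) in the 180 mg and placebo arms. Typical effects under exclusion are smaller. From 9/30 = 30.0%, losing a responder gives 8/29 = 27.6% (−2.4 points), and losing a nonresponder gives 9/29 = 31.0% (+1.0 point). The 120 mg arms are smaller (10 and 8 participants), so their ceilings are 10 and 12.5 points.

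**Illustration of frequency.** The documents give no rate, so let q be the assumed share of collections that fall in the extra days.

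| q | One outside, 2q(1 − q) | Both outside, q² | Both outside if the pair always shifts together, q |
|---|---|---|---|
| 5% | 9.5% | 0.25% | 5%: 1.5 of 30, 1.2 of 24 |
| 10% | 18% | 1% | 10%: 3 of 30, 2.4 of 24 |
| 20% | 32% | 4% | 20%: 6 of 30, 4.8 of 24 |

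The second and third columns assume that the two collections are independent.

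**Illustration of size.** Suppose 9 of 30 reach CRR (30.0%, Clopper-Pearson 95% CI 14.7 to 49.4) and 3 of those responders have both collections outside 2 weeks. The rate becomes 6/27 = 22.2% (8.6 to 42.3) if they leave the denominator, or 6/30 = 20.0% (7.7 to 38.6) if they count as nonresponders.

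**The case against.** **Two weeks is the protocol's definition.** Protocol 8.1.10 and 8.1.11 define the responses with a 2-week window, and the SAP reproduces it faithfully. A sponsor may keep a defined responder criterion while relaxing a continuous endpoint. It stands that the SAP does not misstate the protocol, and that any change must be recorded in 4.8. It does not settle the matter, because the protocol applied the same 2 weeks to the proteinuria collections. The window was not special to the responses, and the SAP gives no reason for splitting it.

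**Collections may not be lost.** Sections 6.1.8, 6.1.10 and 6.1.11 speak of values available at the visit and accept central results from unscheduled visits, and 6.1.5 assigns visits by midpoint windows. A programmer could read these as letting a Day 165 collection count. A reader might infer that out-of-window collections will certainly be discarded. The documents do not say so; it follows only from the literal criterion. Two programmers could therefore report different rates.

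**Aligning the windows loosens the LN composite.** CRR and PRR pair urine with one eGFR value from the 2 weeks before the visit and one from the visit day. The largest gap between a urine collection and an eGFR value would rise from 14 days (Day 169 to Day 183) to 21 (Day 162 to Day 183, or Day 169 to Day 190). In the added week after LN Week 26, background treatment may also change (protocol 6.5.3.1, 6.5.4). Both points stand as small costs. For IgAN at Week 26, 4.2.1 allows no collection after the visit, so its added window does not extend past the point where placebo participants switch to ALXN2050.

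**LN responses differ from percentage reduction by design.** They also need eGFR and no treatment failure, and PRR excludes CRR achievers. That explains different rates. It does not explain a missing status when valid urine exists.

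**Conclusion.** The inconsistency is real and appears in all six response definitions. At Week 26 the responses ignore 14 of the 29 days accepted for LN proteinuria and 7 of the 22 accepted for IgAN. At Week 50 it is 7 of 22 and 14 of 29. One affected participant moves a response rate by at most about 3 points (LN) or 4 points (IgAN) in the main arms.

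This rests on a literal reading of the 2-week criterion and on visits at their nominal days. That the proteinuria window was widened is inferred from the v3.0 history together with the protocol's 2 weeks, since earlier SAP text is not available.

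Two stronger readings are not supported. A reader might infer from the v3.0 change that out-of-window collections were common. The version history says only that the window changed, so the number affected is unknown. A reader might also infer that the main result is at risk. The affected endpoints are secondary and descriptive, without multiplicity adjustment (SAP 4.3), so the primary test, alpha and power are unaffected.

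**What to change.** 1. In SAP 4.3.1.4, 4.3.1.5, 4.3.1.13, 6.1.8, 6.1.10 and 6.1.11, replace the 2-week urine window with the cohort- and visit-specific windows of 4.2.1. Leave the eGFR timing unchanged.
2. State whether a missing response counts as nonresponse or leaves the denominator.
3. List the departure from protocol 8.1.10 and 8.1.11 in SAP 4.8. The 4.2.1 window change is not listed there either and belongs in the same entry.
4. Keep a 2-week version of the responses as a sensitivity summary, to cover the wider gap between urine and eGFR in LN.

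If 2 weeks is intended for the responses, say so with the reason, and state how collections valid only under 4.2.1 are handled.

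The cost is SAP wording and the matching derivation code. No new data are needed. The downside is that urine and eGFR in the LN composite may be up to a week further apart.
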